### **Data analysis:**

The outcomes of the TLUS and laryngoscopy assessments in stage one and stage two and will be analysed using SPSS. 2 x 2 tables will be generated to calculate values of sensitivity (whether a participant can be confirmed as having ILO, or mimicked ILO) and specificity (whether ILO, or mimicked ILO, can be ruled out for a participant), and confidence intervals for visualisation of the vocal folds using TLUS. In stage two, percentage agreement between TLUS and laryngoscopy for confirmation or non-confirmation of ILO will also be calculated.

The values, if available, for measurements of the distance between the arytenoids for healthy volunteers and patients during normal breathing, deep inspiration, and during ILO (mimic in stage 1 and actual in stage 2), will be analysed via a non-parametric comparison of means within SPSS.

Quantitative questionnaire data will be analysed using Microsoft Excel to generate mean values and ranges. Qualitative questionnaire data will be analysed using thematic analysis (Braun and Clarke, 2006), with themes generated to aid understanding of participants' experiences of the TLUS and laryngoscopy procedures.

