## **Aims & Objectives:**

This two-stage pilot study aims to evaluate whether trans laryngeal ultrasound (TLUS) can be a useful tool in the assessment of the abnormal vocal fold movements on inspiration seen in ILO.

The purpose of the two stages of this study is to assess if the use of TLUS is a useful triage screening tool in the assessment of ILO when compared to the current gold-standard reference test of video-laryngoscopy.

Stage one will be conducted with healthy NHS volunteers from the host organisation, (Lancashire Teaching Hospitals NHS Trust) and will look at the degree of success at visualising both vocal cords (right and left), at baseline, during breathing, and when mimicking ILO. The experience of undergoing ultrasound assessment will be looked at via a post-ultrasound scan questionnaire.

Stage two will be conducted with a group of up to 30 patients referred to the Tertiary airways service for breathlessness. We will assess vocal cord movements with simultaneous laryngoscopy (usual care) and TLUS, to investigate whether TLUS has utility as a screening tool to assess the vocal fold movement abnormalities seen in ILO.

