### **Primary aims:**

To perform analysis of the range of vocal fold movements on inspiration, using TLUS in healthy volunteers and patients referred to a tertiary airways service.

To assess the sensitivity, specificity and positive predictive value of the use of ultrasound in the assessment of ILO, using Laryngoscopy as reference standard.

To investigate the patient and healthy volunteer perspectives of TLUS assessment of the vocal cords.

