### **Stage two: patient population**

A sample of 30 participants will be recruited from consecutive patients referred to our NHS Tertiary Airways service for assessment for complex breathlessness and ILO. Participants will be asked at initial assessment, after they have consented to the laryngoscopy, if they would wish to undergo TLUS concurrently with their usual care of diagnostic laryngoscopy.

An information leaflet will be given, and written consent form completed with the patient by the PI. Written Information will be provided at the point of initial consultation (at least 48 hours before the planned procedure. Written consent will take place at the appointment for the Laryngoscopy (usual care for laryngoscopy), by the PI (CS). A witness will not be present. Consent will take place in a private booking-in room that is part of usual care for patients attending for laryngoscopy assessment for ILO). Patients have more than 48 hours to consider the information and decide if they would like to participate.

Patients who require an interpreter for their initial consultation will be provided with information via the interpreter of the study.

Patients will be informed that usual care will not be affected by their decision to participate or not, and that consent can be withdrawn at any point. If the patient finds dual assessment with laryngoscopy and TLUS too invasive or distressing, they can withdraw consent, and the TLUS will be stopped.

It is envisaged that the TLUS operator (PI) will perform the US assessment whilst another SLT completes the laryngoscopy (usual care) and works through the usual diagnostic laryngoscopy provocation protocol to induce symptoms. The US-operating SLT will take a note of settings to achieve image acquisition and will take note of vocal fold movements on an anonymised recording form with subject allocation number identified.

The SLT operators (TLUS and laryngoscopy) will be blinded to the images and results of the other assessment (either TLUS or laryngoscopy), as the screen for the Laryngoscopy system can be rotated away to be unobservable by the US-operator SLT. Following the procedure, the SLT conducting the US will leave the endoscopy theatre room to allow for usual debrief to occur with the patient (usual care). After this, the patient will be asked to complete a short questionnaire electronically to elicit their experience of TLUS.

<https://forms.office.com/pages/designpagev2.aspx?lang=en->

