Following the clinical session, the results of the TLUS and laryngoscopy will be compared for outcome and record made (on the reporting form) of the assessments compared, and any false positive or negative results will be documented, along with ability to visualise either or both vocal folds (left and right).

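### The stage two 2 x 2 tables allow only a positive or negative TLUS result, so accuracy may describe only patients with a usable view, not everyone scanned

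*Combined protocol and SAP*

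**What the plan says.** One of the primary aims is "To assess the sensitivity, specificity and positive predictive value of the use of ultrasound in the assessment of ILO", with laryngoscopy as the reference standard. Under Aims & Objectives, the stated purpose of the two stages "is to assess if the use of TLUS is a useful triage screening tool". For stage two, "A sample of 30 participants will be recruited from consecutive patients referred" to the tertiary airways service; Aims & Objectives puts this as up to 30.

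Under Data analysis, "2 x 2 tables will be generated to calculate values of sensitivity" and specificity, and stage two adds "percentage agreement between TLUS and laryngoscopy for confirmation or non-confirmation of ILO". The same section plans confidence intervals for visualisation of the folds.

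Incomplete views are expected. After the stage two session, "the results of the TLUS and laryngoscopy will be compared for outcome and record made (on the reporting form) of the assessments compared". False positives and negatives are documented then too, "along with ability to visualise either or both vocal folds (left and right"). The Study end definition would close the study early if stage one gave few successful views, without a threshold.

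No section says whether a stage two scan with no usable view is excluded, called negative, called positive or kept as a third result. None says when a one-fold view is enough to call a result.

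**The concern.** In a 2 x 2 table each patient is TLUS positive or negative. A scan with no view is neither, so the simplest way to follow the plan is to leave it out. The accuracy figures then answer a narrower question: how well TLUS performs once a usable view has been obtained. A triage tool has to be judged in everyone to whom it is applied, because a patient whose scan fails still needs a decision. Recruiting consecutive referrals fits that wider question; dropping failed scans gives part of it up.

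The visualisation rate does not repair this. It shows how many scans failed, but not how those patients divide between ILO and non-ILO, nor what sensitivity and specificity are across all scanned patients. A reader of the results could not tell which rule had been applied.

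**Working it through.** **No planned figure to reproduce.** The documents give no expected sensitivity, specificity or visualisation rate, and no justification for the sample of 30. The check therefore applies different rules to one set of assumed data.

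**Inputs.** From the documents: 30 patients (Stage two: patient population). Assumed: 15 with ILO and 15 without; 3 failed scans in each group (6/30 = 20%); one wrong call per group among readable scans.

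- ILO: 11 TLUS positive, 1 negative, 3 not assessable.
- Non-ILO: 1 TLUS positive, 11 negative, 3 not assessable.

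**Formulas.** Sensitivity = correct positives / ILO patients counted. Specificity = correct negatives / non-ILO patients counted. PPV = correct positives / all positives. Agreement = correct calls / patients counted. Counting as wrong means that a failed scan is negative in an ILO patient and positive in a non-ILO patient.

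| Rule for failed scans | Sensitivity | Specificity | PPV | Agreement |
|---|---|---|---|---|
| Dropped | 11/12 = 92% | 11/12 = 92% | 11/12 = 92% | 22/24 = 92% |
| Negative | 11/15 = 73% | 14/15 = 93% | 11/12 = 92% | 25/30 = 83% |
| Positive | 14/15 = 93% | 11/15 = 73% | 14/18 = 78% | 25/30 = 83% |
| Wrong | 11/15 = 73% | 11/15 = 73% | 11/(11+1+3) = 11/15 = 73% | 22/30 = 73% |

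Exact (Clopper-Pearson) 95% intervals: 11/12, 62% to 100%; 11/15, 45% to 92%; 22/24, 73% to 99%; 22/30, 54% to 88%. The visualisation rate is 24/30 = 80% (61% to 92%) under every rule, so it cannot tell them apart.

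**Direction depends on who fails.** Two extreme splits of the same 6 failures show this.

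- No failed scan has ILO (ILO 14 positive, 1 negative; non-ILO 1 positive, 8 negative, 6 failed). Negative coding leaves sensitivity at 14/15. Positive coding takes specificity from 8/9 (89%) to 8/15 (53%) and PPV from 14/15 (93%) to 14/21 (67%).
- All failed scans have ILO (ILO 8 positive, 1 negative, 6 failed; non-ILO 1 positive, 14 negative). Positive coding leaves specificity at 14/15 and raises PPV from 8/9 (89%) to 14/15 (93%). Negative coding takes sensitivity from 8/9 (89%) to 8/15 (53%).

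So negative coding lowers sensitivity only if some failed scans have ILO, and positive coding lowers specificity only if some do not. PPV is the same under dropping and negative coding, because only positive calls enter it.

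**Size by failure rate.** With accuracy 0.9 when seen and failure fraction f equal in both groups, count-as-wrong sensitivity and specificity are each 0.9 x (1 - f): 81% at f = 10%, 72% at 20%, 63% at 30%. The chance of at least one failed scan in 30 is 1 - (1 - f)^30: 79% at f = 5%, 96% at 10%, 99.9% at 20%.

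**The case against.** **The wording may already cover these scans.** A no-view scan could be read as non-confirmation of ILO in the agreement measure. Taken literally, the sensitivity and specificity definitions ask whether ILO can be confirmed or ruled out, and such a scan does neither. A one-fold scan may still be called by the operator. This stands in part: the text is ambiguous rather than explicit about exclusion, and for one-fold scans only the adequacy criterion is missing. But these readings lead to different rows of the table, so the rule still has to be written down.

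**The information is not lost.** View status is recorded per patient and images are stored, so scans could be recoded later. A second reader handles uncertain findings, though this is described under stage one and for a proportion of scans. This makes the gap repairable. What it does not supply is a rule fixed in advance.

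**This is a small pilot.** In the example, 73% lies inside the visualised-only interval for sensitivity (62% to 100%). That limits how much weight any figure can bear. It does not remove the point: the interval expresses sampling error, while the shift comes from an unstated rule applied to identical scans.

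**Stronger readings.** A reader might infer that failed scans will be classified with the laryngoscopy result known, because visualisation is mentioned at the comparison step. The documents do not support this: the blinded operator already notes fold movements on a form during the scan, the comparison presupposes a TLUS result, and the form is not in the text. A reader might also extend the point to the stage one mimicked-ILO table. That is weak, because success in seeing the cords is itself a stage one outcome, and the instruction to start the tasks once the cords are seen may describe only timing.

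**Conclusion.** The point holds for stage two. The planned tables allow two TLUS results, the protocol expects that some views may fail, and no rule connects the two. Following the layout most naturally gives accuracy in patients with a usable view, which is not the group that the triage purpose concerns.

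In the worked example, dropping failed scans reports 92% for sensitivity, specificity and agreement, where counting them as wrong gives 73% for each, a difference of about 18 percentage points (91.7 - 73.3 = 18.4). This rests on an assumed 20% failure rate spread evenly between groups, half the patients having ILO, and the assumed accuracy of readable scans. With few failures the effect is small. The early-closure criterion makes a very high failure rate less likely, but sets no limit.

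It would go too far to infer that every coding of failed scans lowers accuracy. Negative or positive coding credits some failed scans as correct unless they all fall in the group that coding penalises, and sensitivity or specificity may stay unchanged or rise. Nor do the documents support any particular adequacy rule, such as requiring both folds. The missing rule is certain; its numerical effect is conditional.

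**What to change.** Before stage two starts, amend the Data analysis section as follows.

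- Replace the stage two 2 x 2 table with a 3 x 2 table: TLUS positive, negative or not assessable, by laryngoscopy ILO yes or no.
- Have the sponsor set an adequacy criterion in advance, including when a one-fold view counts. The operator marks one of the three results on the stage two recording form before the results are compared.
- Name one coding of not-assessable scans for the main analysis in all scanned patients, covering sensitivity, specificity, PPV and agreement.
- Give the count-as-wrong result as the worst-case sensitivity analysis, since negative or positive coding alone can hide it (25/30 agreement against 22/30 in the example).
- Show visualised-only figures as secondary, beside the visualisation rate. Use exact confidence intervals throughout.

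The cost is a change of analysis wording and one three-option item on a form that the operator already completes. No extra patients, scans or procedures are needed. The downside is a few more figures from a small sample, some less favourable than the visualised-only ones.

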## **Proposed methods:**

### **Stage one: healthy controls:**

Volunteers will be recruited from NHS staff at the host organisation (LTHTR). Healthy volunteers will be given an information leaflet and consent form upon providing an expression of interest.

Informed consent will be taken by the PI from healthy volunteers who decide to go ahead. It will be stressed that participation and consent can be withdrawn at any time. The consent process itself will take place before the procedure and will be taken by the PI (CS). Consent will be taken in a separate and private room (either the booking-in room in the endoscopy department at RPH, or a separate clinic room in the chest Clinic). This will be completed before the procedure and before entry into the room where the ultrasound procedure will take place.

The consent forms will be stored in a locked cabinet in PI's office. Longer-term, study documents including data and investigator site files will be archived at the Trust's off site archiving facility following local procedures.

Healthy volunteers will be allocated a time and date to attend Chest clinic, or the Endoscopy department at the host organisation, Royal Preston Hospital (RPH) for the scanning session. The scan will be carried out in a private room using transmission gel. Access only to the neck area is required, with privacy and dignity always respected.

The PI will perform an US scan of the larynx, using the Vscan Air (GE), using a protocol designed by the PI. The scan is recorded and stored securely using GE's system. A proportion of scan will be sent to the study collaborator ([name]) and a Specialist Head & Neck Sonographer securely and anonymously with no patient identifiable information included in order to confirm findings when there is uncertainty, and in order to ensure inter-rater reliability.

The scan will consist of a "sweep" of the larynx to identify the main landmarks (hyoid bone, thyroid cartilage, arytenoid cartilages, vocal cords and false vocal cords). A recording form has been prepared for ease of recording. An anonymised code number will be assigned to the Healthy volunteer.

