A record will be taken of the frequency in MHz and depth that successful visualisation of the vocal cords occurred to help inform future studies and refine the protocol. Any other factors that are deemed useful to include to help replicate findings and improve image quality and scanning success will also be recorded (such as gain used, high or low, and approach transverse, or lateral longitudinal, and the use of any pre-sets such as Neo-head, lung or small parts).

When the vocal cords are visualised, the healthy volunteer will be asked to breathe normally, take 3 deep inspirations, and then, say “ee” for a sustained period. They will then be asked to breath hold, then take a deep breath in (3 trials), and then mimic ILO (the PI will discuss how to do this before the scan takes place). The commands for each of the above will be in the same order for each patient, as there is no accompanying sound, this will allow for easier analysis to be able to differentiate each vocal cord movement according to what the volunteer was asked to do.

Following the procedure, the volunteer will be given an electronic questionnaire to complete, so that feedback on their experience can be gained and used as part of writing up of findings.

[https://forms.office.com/pages/designpagev2.aspx?lang=en-US&origin=OfficeDotCom&route=Start&subpage=design&id=gmOokJ\\_8nEW5GphS-wiyzcd-VqpQSdVGguxTgVT2MfRUMEZUNUoxT1YyQkIPOEVVM0VQVVpJRUVEUS4u](https://forms.office.com/pages/designpagev2.aspx?lang=en-US&origin=OfficeDotCom&route=Start&subpage=design&id=gmOokJ_8nEW5GphS-wiyzcd-VqpQSdVGguxTgVT2MfRUMEZUNUoxT1YyQkIPOEVVM0VQVVpJRUVEUS4u)

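### Stage one, as designed, cannot give the participant-level sensitivity and specificity for mimicked ILO that the Data analysis section plans

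*Combined protocol and SAP*

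**What the plan says.** The Data analysis section of the combined protocol and SAP opens with both tests in both stages: "The outcomes of the TLUS and laryngoscopy assessments in stage one and stage two and will be analysed using SPSS". It then plans 2 x 2 tables. Sensitivity is defined as confirming true or mimicked ILO in a participant, and specificity as "specificity (whether ILO, or mimicked ILO, can be ruled out for a participant". The same section later assigns the mimic to one stage: "during ILO (mimic in stage 1 and actual in stage 2". The sentence on percentage agreement between the two tests is limited to stage two; the sentence on the 2 x 2 tables is not.

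Other sections describe stage one differently:

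- **Aims & Objectives:** stage one "will look at the degree of success at visualising both vocal cords (right and left), at baseline, during breathing, and when mimicking ILO". Laryngoscopy enters with stage two: "We will assess vocal cord movements with simultaneous laryngoscopy (usual care) and TLUS".
- **Primary aims:** accuracy is to be assessed "using Laryngoscopy as reference standard".
- **Stage one: healthy controls:** the investigator scans the larynx, gives the commands in one fixed order, and finally asks the volunteer to "mimic ILO (the PI will discuss how to do this before the scan takes place"). A questionnaire follows. No laryngoscopy and no group that does not mimic are described.
- **Stage two: patient population:** simultaneous laryngoscopy, mutual blinding of the two operators, and the recording of false positives and negatives appear here only.

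**The concern.** Sensitivity needs participants who have the condition according to a reference, and specificity needs participants who do not. The analysis text promises both for mimicked ILO, but the stage one methods supply neither a reference test nor volunteers without the target condition. This is a stated analysis that the described design cannot deliver, rather than a missing detail.

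The figure that could still be printed, the share of mimics read as positive, is also weak. Nothing described confirms that a coached mimic actually narrowed the glottis. The investigator who coaches the mimic also performs the scan, knows the command order and analyses the data. Reported under the name of sensitivity, this share could be taken as evidence that ultrasound detects ILO, which is a primary aim and which the protocol ties to laryngoscopy.

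**Working it through.** The documents state no stage one sample size and no expected accuracy, so there is no figure to reproduce. The check counts the denominators of the planned table.

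**Inputs**

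- Unit: the participant (both definitions in Data analysis).
- Target: true or mimicked ILO, the mimic belonging to stage one (Data analysis).
- Reference standard: laryngoscopy (Primary aims).
- Stage one procedures: scan and questionnaire, same commands in the same order, mimic last (Stage one: healthy controls).
- Stage one size: not stated; call it n.

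**Formulas**

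Sensitivity = TP / (TP + FN). Specificity = TN / (TN + FP).

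**Participant as unit, by choice of reference**

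1. *Command to mimic.* All n volunteers are positive, so TP + FN = n. Negatives are n − n = 0, so specificity = 0/0 whatever n is. Sensitivity has a denominator, but a reader who called every scan a mimic would score n/n = 100% with no penalty.
2. *True ILO, volunteers presumed free of it.* Positives are 0, so sensitivity = 0/0. Specificity has denominator n.
3. *Laryngoscopy, as the primary aim requires.* No stage one result is described, so none of the four cells can be filled.

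The commands are given once the cords have been seen. A volunteer whose cords are never seen supplies no ultrasound reading of a mimic, and so adds no usable negative under reading 1.

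**Manoeuvre as unit**

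The sequence gives each volunteer 3 + 3 = 6 deep inspirations besides the mimic, so 6 correlated negatives per volunteer are available. With one mimic and one normal-breathing segment per volunteer, both denominators would be n. If all n were read correctly, the exact 95% lower limit would be 0.025^(1/n): 69.2%, 83.2% and 88.4% for n = 10, 20 and 30 (assumed sizes). Such a table can therefore be estimated, but the plan does not define it and the mimic would still be unverified.

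**The case against.** Several points can fairly be made for the plan.

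- *The opening sentence of Data analysis is garbled and may mean ultrasound in stage one and both tests in stage two.* This is plausible and softens the laryngoscopy conflict. It does not help the 2 x 2 tables, because mimicked ILO is named in the specificity definition itself.
- *The fixed command order is there so that movements can be told apart, which points to a per-manoeuvre analysis.* It may do so. The definitions nevertheless name the participant, and no manoeuvre table, masked reading or allowance for repeated observations is given.
- *A volunteer who fails to mimic could count as a negative.* In principle yes, but no independent check of success or failure is described.
- *Second readers exist.* A proportion of scans goes, anonymised, to a collaborator and a specialist sonographer, for uncertain findings and for inter-rater reliability. This is a real but partial safeguard: masking to the command is not stated, and a second reading of the same scan is not a reference test.
- *Nothing depends on stage one accuracy.* The stage one objectives are visualisation and participant experience, the early-closure rule in Study end definition rests on how often the folds are seen, and Data analysis already plans confidence intervals for visualisation. This stands and limits the seriousness of the point.

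Two stronger readings are tempting. A reader might infer that stage one specificity is 0/0 without qualification. That holds only with the command as reference and the participant as unit; the plan fixes the unit but not a stage one reference. A reader might also infer that coached mimics will inflate the stage two accuracy figures. That requires pooling, which the documents nowhere propose: volunteers and patients carry different codes, and the analysis text distinguishes the mimic of stage 1 from the actual ILO of stage 2. Pooling is not ruled out, but there is no basis for putting a size on it.

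**Conclusion.** The point holds and should be fixed. On the methods as written, stage one cannot yield a valid participant-level pair of sensitivity and specificity under any of the three references, whatever the number of volunteers. The defect is structural, so no percentage or sample size attaches to it.

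The conclusion assumes that stage one has no laryngoscopy, as its methods describe, that the unit is the participant, as the definitions say, and, for the true-ILO reading, that healthy volunteers are free of ILO. The damage is confined to stage one: the primary accuracy comparison in up to 30 patients stands as long as stage one data stay out of its tables.

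**What to change.** In Data analysis:

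1. Restrict the 2 x 2 tables, sensitivity and specificity to stage two, with laryngoscopy as reference.
2. Delete mimicked ILO from both definitions and state that stage one data do not enter these tables.
3. Reconcile the mention of stage one laryngoscopy outcomes with the stage one methods.
4. For stage one, report the proportion of all scanned volunteers with both folds visualised, with the confidence intervals already planned, counting folds not seen as not visualised. Where the recordings allow, give this at baseline, during breathing and when mimicking, with the number of volunteers who reached each condition.
5. If a mimic-versus-breathing comparison is kept, define it per manoeuvre, allow for repeated observations within a volunteer, have the external readers already named in the stage one methods read it masked to the command, and do not call it accuracy for ILO.

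The cost is mainly wording, and the sponsor loses only a figure that could not be interpreted. The stage one recording form is not in the documents, so some stored scans may need re-reading to give visualisation by condition. Item 5, if chosen, adds reading time for the external readers.
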